## 1.1 Background

The study discussed below was conducted by Bayhill Therapeutics with the investigational product designated as BHT-3021 (Roep et al. 2013). BHT-3021 was acquired from Bayhill by Tolerion, Inc. and has been renamed TOL-3021. Bayhill Therapeutics conducted a clinical randomized dose escalation study in which 80 subjects with established T1D diagnosed within 5 years were enrolled in a randomized dose escalation study to evaluate treatment with 0.3 mg, 1.0 mg, 3.0 mg, 6.0 mg BHT-3021 or placebo administered with a weekly intramuscular (IM) injection for 12 weeks.

Subjects were screened for eligibility within 6 weeks prior to randomization. Subjects were randomized to BHT-3021 or placebo in a 2:1 ratio and entered the Blinded Treatment Period, when BHT-3021 or placebo was administered via weekly IM injection for 12 weeks (Weeks 0 to 11). Four weeks after the last dose of BHT-3021 or placebo (Week 15), subjects underwent a complete evaluation for safety, pancreatic function, and anti-insulin responses. Subjects were monitored for safety and immune response in a blinded fashion for 12 months after the first dose of BHT-3021 or placebo (the Blinded Evaluation Period). Each subject's treatment assignment was then unblinded. Subjects who received BHT-3021 were invited to enter a 12-month Long-Term Follow-Up (LTFU) Period, during which they were monitored for delayed adverse events, pancreatic function, and immune response. Subjects who received placebo were eligible for cross over to receive 12 weeks of treatment with BHT-3021 in an open-label manner. The dose of BHT-3021 during the Open Label Cross Over Period was the "best dose," defined as the dose or doses already administered in the clinical trial that the Data Safety Monitoring Board (DSMB) found to have an acceptable safety profile and which the Sponsor determined at the time of cross over to present the best balance of safety, biological activity (immune response), and/or efficacy. More than one dose could have been designated as a "best dose," as long as all doses presented comparable safety and efficacy profiles. Cross over subjects were fully evaluated at the end of the dosing period (Week 15), after which they entered the Open Label Evaluation Period that lasted for 12 months after the first dose of BHT-3021. Finally, the subjects were entered in the 12-month LTFU Period.

Out of the eighty subjects enrolled in the study, the initial 9 subjects were enrolled into an open-label cohort. After completion of the dose-finding phase of the study (Dose Escalation Phase), additional subjects were enrolled to expand one or more dose cohorts in order to obtain additional safety and efficacy data (Expansion Phase). A schematic of the study design is presented in Figure 1 below.

**Figure 1. Study Schematic Protocol BHT-3021**

The dose escalation portion of the study enrolled subjects sequentially into the 1.0 mg cohort, followed by the 3.0 mg cohort, and then the 0.3 mg and 6.0 mg dose level cohorts concurrently. All cohorts were randomized in an active: placebo 2:1 ratio. After the dose escalation enrollment was complete, additional subjects were randomized (active: placebo 2:1) into the Expansion Cohort to receive BHT-3021 at doses of 0.3 mg, 1.0 mg, or 3.0 mg, or to placebo. Table 1 shows the number of subjects randomized by study phase and dose.

**Table 1. Subject Randomization by Study Phase and Dose**

Dose Administered	Number of Subjects Randomized			Placebo Subjects Crossed Over
	Dose Escalation Phase	Expansion Phase	Total in Cohort	
0.3 mg	6	8	14	
1.0 mg	10	8	18	7
3.0 mg	8	6	14	6
6.0 mg	8	0	8	
Placebo	16	10	26	
Total	48	32	80	13

[figure not shown]
Subjects were required at screening to have a stimulated C-peptide level of  $\geq 0.20$  nmol/L and the presence of antibodies to at least one of the following: insulin and GAD65, or IA-2. They also had to agree to intensive management of diabetes with a goal of HbA1c  $\leq 7.0\%$ . While the primary objective of the study was to evaluate the safety of BHT-3021, exploratory efficacy outcomes of stimulated C-peptide, insulin requirements, glucose levels, and HbA1c were included. Additionally, immunological outcomes of insulin, GAD65, and IA-2 antibodies, as well as T-cell response to diabetes-related antigens, were measured. After completion of the 12-week blinded treatment and overall blinded evaluation at Week 15, subjects entered a long-term follow-up period of 12 months from initial dosing, with visits at 6, 9, and 12 months, during which investigators and subjects remained blinded. Subjects randomized to placebo had the option to receive open-label active treatment with BHT-3021 1.0 mg or 3.0 mg and proceeded with 12 weeks of treatment and follow-up at Week 15 as in the original study design. Subjects were then followed for the 12-month post-treatment evaluation.

BHT-3021 was well tolerated at all doses studied. There was no suggestion of drug-related toxicity at any dose of BHT-3021 studied based on the severity and relationship of reported adverse events (AEs) graded according to the NCI Common Toxicity Criteria for Adverse Events (CTCAE). A high percentage of subjects experienced at least 1 treatment emergent adverse event (TEAE) during the study, but a relatively small percentage of these were Grade 3 or higher. Nearly all TEAEs reported were of mild severity and half or more were considered unrelated to treatment. Thirteen TEAEs of Grade 3 or higher were all considered unrelated to treatment and none of the events required expedited reporting.

The ANA and anti-dsDNA results suggest that BHT-3021 administration is not associated with an immune response against DNA.

C-peptide, which is an important surrogate marker for pancreatic secretion of insulin, was measured at Week 5 during treatment and at Week 15 (4 weeks following treatment). Measurements were repeated at 6 and 12 months during the LTFU. As shown in Figure 2, C-peptide levels increased over baseline levels, most noticeably in the BHT-3021 1.0 and 3.0 mg treatments groups compared to placebo. At Week 15, the increase over baseline seen at 1.0 mg was significant compared to placebo ( $p < 0.026$ ), with an increase of 19.5% compared to a decrease 8.8% in placebo. In subjects who responded with an increase over baseline in C-peptide at Week 15, 8 of 15 subjects treated with 1.0 mg BHT-3021 continued to show an increase of C-peptide at 6 months, while 9 of 17 subjects treated with 3.0 mg showed an increase at 6 months.

**Figure 2. Mean Percent Change in C-Peptide AUC**

HbA1c levels varied at baseline, reflecting differences among subjects in glycemic control, but remained fairly constant through Week 15. Overall, subjects treated with BHT-3021 tended to have lower HbA1c levels at Week 11 compared to placebo ( $p < 0.08$ ). Levels tended to rise after that with no significant differences among treatment groups. Use of insulin fell during dosing in the 1.0 mg treated group but was not statistically significant compared to placebo. Insulin use was stable among the other groups during dosing. Usage in all groups increased during follow-up, likely reflective of the increases in HbA1c and/or declining endogenous insulin secretion.

Immunological studies were conducted to quantify changes in islet-specific CD8+ T cells during treatment. Data from 41 of 80 subjects were available at baseline and at least 1 other data point after treatment for this analysis. Results of these investigations indicated that BHT-3021 induced antigen-specific reductions in CD8+ cells reactive to proinsulin but not to other antigens, including viral antigens. The magnitude of the reduction was inversely correlated with the improvement in C-peptide.

Autoantibodies to pancreatic antigens were measured at baseline and Week 15. Few changes in antibody status between baseline and Week 15 were noted. One placebo-treated subject converted from negative to positive for GAD65. Two active- and placebo-treated

subjects converted from negative to positive for insulin antibodies. An evaluation of C-peptide in these subjects showed no consistent changes that correlated with induction of IAs. No subjects converted from negative to positive for IA-2.

Based on analysis of serum C-peptide levels, laboratory data, and antibody responses to pancreatic autoantigens, there is no evidence that any of the doses of BHT-3021 caused an increase in autoimmunity with resultant acceleration of pancreatic beta cell loss in any subject. An increase in autoimmunity is a theoretical concern with a DNA vaccine; it is reassuring that this was not seen in this study of 80 subjects dosed for up to 12 weeks with BHT-3021. These results provide preliminary evidence that TOL-3021 may be efficacious in the preservation of  $\beta$ -cell function in T1D subjects.

The study also suggested a good safety profile, which was just as important as the efficacy findings. No deaths were reported in the study. Serious Adverse Events (SAEs) that were reported were all considered unrelated to treatment and included the following: 2 subjects treated with 3.0 mg (diabetic ketoacidosis, Grade 1; infection/abscess natal cleft, Grade 3), 1 treated with 1.0 mg (hemiparesis, Grade 1) and 4 treated with placebo (abdominal pain, Grade 3; elevated blood pressure and premature uterine contraction, Grade 1; migraine, Grade 1; neurologic presentation secondary to a primary cardiac abnormality, Grade 1). Two subjects treated with 3.0 mg discontinued the study due to possibly related AEs of headache and vaginal candidiasis. An overall summary of TEAEs can be found in Table 2 and a summary by MedDRA Body System in Table 3.

**Table 2. TEAE Overall Summary by Subject**

TEAEs by Subject	0.3 mg n=14 n (%)	1.0 mg n=18 n (%)	3.0 mg n=14 n (%)	6.0 mg n=8 n (%)	Placebo n=26 n (%)
Any TEAE	12 (85.7)	18 (100.0)	11 (78.6)	7 (87.5)	25 (96.2)
$\geq$ Grade 3	0 (0.0)	4 (22.2)	2 (14.3)	3 (37.5)	4 (15.4)
Possibly Related	5 (35.7)	6 (33.3)	6 (42.9)	4 (50.0)	6 (23.1)

**Table 3. TEAE Summary by MedDRA Body System**

MedDRA Body System	0.3 mg n=14 n (%)	1.0 mg n=18 n (%)	3.0 mg n=14 n (%)	6.0 mg n=8 n (%)	Placebo n=26 n (%)
Subjects with Any TEAE	12 (85.7)	18 (100.0)	11 (78.6)	7 (87.5)	25 (96.2)

MedDRA Body System	0.3 mg n=14 n (%)	1.0 mg n=18 n (%)	3.0 mg n=14 n (%)	6.0 mg n=8 n (%)	Placebo n=26 n (%)
Blood and Lymphatic System Disorders	1 (7.1)	0 (0.0)	3 (21.4)	0 (0.0)	1 (3.8)
Cardiac Disorders	0 (0.0)	0 (0.0)	0 (0.0)	1 (12.5)	1 (3.8)
Ear and Labyrinth Disorders	0 (0.0)	0 (0.0)	1 (7.1)	0 (0.0)	0 (0.0)
Eye Disorders	1 (7.1)	2 (11.1)	1 (7.1)	0 (0.0)	2 (7.7)
Gastrointestinal Disorders	2 (14.3)	6 (33.3)	5 (35.7)	1 (12.5)	6 (23.1)
General Disorders and Administration Site Conditions	2 (14.3)	1 (5.6)	1 (7.1)	3 (37.5)	1 (3.8)
Immune System Disorders	1 (7.1)	0 (0.0)	0 (0.0)	0 (0.0)	4 (15.4)
Infections and Infestations	10 (71.4)	13 (72.2)	9 (64.3)	6 (75.0)	13 (50.0)
Injury, Poisoning, and Procedural Complications	3 (21.4)	3 (16.7)	3 (21.4)	2 (25.0)	4 (15.4)
Investigations	1 (7.1)	1 (5.6)	2 (14.3)	1 (12.5)	3 (11.5)
Metabolism and Nutrition Disorders	3 (21.4)	2 (11.1)	3 (21.4)	3 (37.5)	12 (46.2)
Musculoskeletal and Connective Tissue Disorders	2 (14.3)	1 (5.6)	4 (28.6)	1 (12.5)	3 (11.5)
Nervous System Disorders	4 (28.6)	6 (33.3)	5 (35.7)	2 (25.0)	8 (30.8)
Psychiatric Disorders	0 (0.0)	0 (0.0)	2 (14.3)	0 (0.0)	1 (3.8)
Renal and Urinary Disorders	1 (7.1)	1 (5.6)	0 (0.0)	0 (0.0)	0 (0.0)
Respiratory, Thoracic, and Mediastinal Disorders	1 (7.1)	3 (16.7)	4 (28.6)	1 (12.5)	8 (30.8)
Skin and Subcutaneous Tissue Disorders	3 (21.4)	4 (22.2)	3 (21.4)	2 (25.0)	8 (30.8)
Surgical and Medical Procedures	0 (0.0)	1 (5.6)	0 (0.0)	0 (0.0)	1 (3.8)

## 1.2 Rationale for the Study

The phase 2a study (BHT-3021) as discussed in the Background (Section 1.1) provided evidence of the safety and efficacy of TOL-3021. None of the SAEs reported were

determined to be related to the study drug at any of the doses tested. Most of the TEAEs reported were mild. Evaluation of the injection site reactions revealed only one report of an injection site reaction and reports in four subjects of injection site pain, providing evidence that TOL-3021 administered as an IM injection is well tolerated.

Given the evidence from the phase 2a study supporting both safety and efficacy, the SUNRISE study is being conducted to further evaluate the safety and continue to explore the efficacy of TOL-3021 1.0 mg in subjects with new onset or established T1D. The SUNRISE study will also enable enrollment of adolescents (aged 12.0 to <18.0 years) in SUNRISE and other TOL-3021 studies.

The treatment effect of TOL-3021 dosing over 24 weeks and subsequently over 52 weeks on preserving endogenous insulin secretion as reflected by C-peptide secretion and its effect on other measures of efficacy will be explored. The mean C-peptide area under the curve (AUC) during a 4-hour mixed-meal tolerance test (MMTT) will be evaluated during the study at Weeks 12, 16, 24, and 52. This is the appropriate outcome for both clinical and regulatory purposes (Palmer et al. 2004). C-peptide is a useful and widely used method of assessing pancreatic  $\beta$ -cell function (Jones and Hattersley 2013). C-peptide is the part of proinsulin that is cleaved prior to co-secretion with insulin in equimolar amounts. Unlike secreted insulin, which is variably cleared by the liver, C-peptide passes through the liver without any uptake. C-peptide is cleared in the peripheral circulation at a constant rate and has a half-life of 20-30 minutes, while insulin has a half-life of only 3-5 minutes. C-peptide is also not contained in the insulin therapeutic products subjects will receive to manage their diabetes. For these reasons, C-peptide is widely used as the preferred measure of endogenous insulin secretion (Yosten et al. 2014, Leighton et al. 2017).

The most reliable measurement of endogenous insulin secretion and  $\beta$ -cell function is measurement of C-peptide under standardized conditions. The amount of preserved C-peptide is positively correlated with improved clinical outcomes. C-peptide levels post-stimulation are a validated means of assessing endogenous insulin secretion. Sensitive, reproducible assays for measuring C-peptide are readily available (Jones and Hattersley 2013).

In 2001, the National Institutes of Health (NIH) established the Type 1 Diabetes TrialNet to conduct studies of therapies aimed to preserve  $\beta$ -cell function in subjects with recently diagnosed T1D and to prevent diabetes in subjects at increased risk of future T1D. TrialNet has adopted C-peptide as the principal outcome measure for clinical trials of interventions against T1D autoimmunity (Palmer et al. 2004). In the SUNRISE study, the change in C-peptide AUC during the MMTT at baseline, during treatment, and at the end of the study end will be compared between the control group and those receiving active therapy in patients who have been diagnosed with T1D within 5 years of study enrollment. The trials

may also demonstrate a clinically meaningful reduction in mean daily insulin requirements accompanied by similar or better glycemic control in those actively treated compared to the control arm (FDA 2008). FDA's position on the primary outcome would presumably apply also to trials of established T1D patients.

## **2 OBJECTIVES**

### **2.1 Primary Efficacy Objective.**

To evaluate the effect of TOL-3021 dosing over 24 weeks on preserving endogenous insulin secretion as reflected by C-peptide secretion, and its effect on other measures of efficacy in patients with Type 1 Diabetes Mellitus (T1D).

### **2.2 Safety Objective**

To evaluate the safety of TOL-3021 administered as weekly intramuscular (IM) injections over 52 weeks in patients with Type 1 Diabetes Mellitus (T1D).

## **3 TRIAL DESIGN**

The SUNRISE study is a prospective, multi-center, randomized, placebo-controlled trial in subjects aged 12.0 to <41.0 years diagnosed with T1D, as defined by ADA criteria, and within 5 years of diagnosis. Time of diagnosis is defined as the first day of insulin administration. The study is triple-blind through the analysis at Week 24, after which the Sponsor will be group unblinded. The study will continue through Week 52 as double-blind with site staff and subjects blinded. Subjects will be stratified by duration (zero up to 1 year and 1 year up to five years) to ensure balance of disease duration across treatment and placebo groups in each strata. For analytical purposes, all subjects 12-<41 will be considered cohort A, subjects aged 12-<18 will be considered cohort B and subjects aged 18-<41 will be considered cohort C. For subjects aged 12-<18 (Cohort B), dosing will be staggered with an initial 6 subjects aged 14-<18 being enrolled with the last subject having a minimum of 2 injections with at least 1 week follow-up after the 2nd injection. Safety data from this cohort will be evaluated before opening the study subjects 12 and older. Subjects should be randomized no sooner than 6 weeks after diagnosis, unless blood glucose is adequately controlled as indicated by time in range >55% with CGM. Screening assessments will include a physical examination, a fundus photography examination, chemistry and hematology safety labs, urinalysis, urinary protein screen (if positive a 24-hour collection for urine protein and creatinine will be obtained), HbA1c, presence of T1D antibodies, and a MMTT. Up to 99 qualified subjects who meet all selection criteria will be randomized in a 2:1 ratio to treatment with TOL-3021 or placebo and treated for 52 weeks (Figure 3). Subjects will agree to diabetes management during the

study with the goal of maintaining HbA1c levels of approximately 7.0% without frequent episodes of hypoglycemia.

Study drug treatments will be administered via an IM injection into a large muscle every week for 52 weeks. Initial treatments will be administered at the clinical site at randomization and at the Week 1 and Week 2 visits. During those visits, subjects and/or a caregiver will be trained to administer study drug at home in subsequent weeks. Study drug will be dispensed at the Week 2 visit for Week 3 administration at home (with the exception of the first 6 subjects aged 14- <18 to be enrolled in cohort B who will have drug administered at the clinical site), and at Weeks 4, 8, 12, 16, 20, 24, 28, 32, 36, 40, 44, and 48 for at home administration.

Subjects will have screening and randomization visits, followed by regular visits to the clinic, for efficacy evaluations and safety assessments throughout the 52-week study. A 4-hour MMTT will be conducted during screening, as part of a single-day visit or conducted on a separate day. If the screening visit procedures will be conducted in a single day the subject must be using their own CGM, and able to share that data with site coordinator to confirm if time in range has been met for 3 of 5 consecutive or non-consecutive days prior to confirmation of a single screening visit. Subjects will be provided with instructions for preparing for the MMTT prior to the visit when it will be conducted. Subjects with peak C-peptide during the screening 4-hour MMTT < 0.150 nmol/L will not be enrolled. The randomization visit must be at least 3 days after the screening MMTT. The screening results will be the baseline value for the MMTT. Continuous glucose monitoring (CGM) will be initiated within 5 days prior to the screening MMTT visit and continued through Week 52. If CGM recordings are inadequate during week 50-52, CGM may be continued until the Week 54 visit. The study will allow subjects to be unblinded to interstitial glucose data from the CGM device to minimize any risk to subjects. Site research staff will train subjects or their caregivers on appropriate use and associated risks of using a CGM device.

A Data Safety Monitoring Board (DSMB) was established prior to study initiation to review data throughout the study, including the 12-week data described below.

[figure not shown]
When the first 30 treated subjects completed the Week 12 visit, all available data was compiled and provided to the DSMB to consider if the enrollment of adolescent subjects in TOL-3021 studies can be recommended. Summary and individual subject data were provided for DSMB and FDA review. The DSMB confirmed that the protocol can be amended to include subjects aged 12 - < 18 years of age and submitted to FDA. If no objection is received from regulators and IRBs, sites will be notified that they may begin enrollment of subjects aged 12 - <18.

Subjects and investigators will be blinded to treatment assignment throughout the study. Selected Emmes staff will have access to treatment assignments. The primary data analysis will be conducted on data collected through Week 24. Cohorts B and C may be analyzed

separately. An interim analysis will be completed after the first 30 patients have completed 24 weeks. Results of the interim analysis will be shared with the DSMB and with a limited number of Tolerion staff, not directly involved in running the trial. Unblinded data summaries including safety outcomes and efficacy assessments will be prepared for the sponsor during the study using all data collected through Week 36. Final analysis of the data will be conducted at 52 weeks. The data summaries are unblinded to Sponsor and Emmes, the CRO, only.

Subjects will continue in the study for a 2-year safety follow-up period after completion of the 52-week double-blind study. During this 2-year follow-up subjects will have clinic visits at 18, 24, and 36 months from their first dose in the double-blind study to evaluate safety. At each of these follow-up visits a MMTT will be administered. Subjects may also be offered the opportunity to continue on study medication in a follow-on protocol for one or more years. Any follow-on study will continue to monitor subject safety in line with the requirements of the SUNRISE protocol.

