	
results will be provided to the DSMB. Primary analysis of the data will be conducted after all randomized participants have completed 24 weeks Cohorts B and C may be analyzed separately. Unblinded data summaries including safety outcomes and exploratory efficacy assessments will be prepared for the sponsor during the study using all data collected through Weeks 24 and 36.

Pharmacokinetic considerations	N/A
Statistical Analyses	
Analysis Populations
 
Safety The safety population will consist of all subjects who receive one or more doses of TOL-3021 or placebo and have any follow-up safety data.
 
Efficacy The efficacy population is by intention-to-treat: all subjects randomized to treatment and taking at least one dose of medication will be included in the ITT population. Appropriate imputation methods may be used for missing data.
 
Statistical Methods
 
Primary Efficacy Analysis
 
The analysis of the primary outcome, change from baseline in log-transformed MMTT-stimulated 4-hour mean C-peptide AUC at multiple time points will test the null hypothesis of “no treatment group difference” versus the two-sided alternative using the intent-to-treat (ITT) cohort. The primary hypothesis test will be the treatment group estimate from a repeated measures mixed model fit to a log-transformed 4-hour C-peptide AUC response at 12, 16 and 24 weeks, adjusted for the baseline C-peptide AUC, age group and duration group.

Estimated Trial Initiation Date	10 June 2019
Estimated 52-Week Trial Completion Date	30 Sep 2021
Estimated Follow-up Period Completion Date	30 Sep 2023

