### 13.2 Interim Data Analysis

When the first 30 treated subjects have completed the Week 12 visit, summary and individual safety data will be submitted to the DSMB for review to support expanding enrollment in TOL-3021 studies to adolescent subjects aged 12.0 to <18 years of age.

An interim analysis will be performed when the first 30 subjects complete 24 weeks of treatment. The DSMB will review data in a blinded manner. Alpha spending will be utilized by the O'Brien-Fleming method, with 0.0052 of the alpha being spent at the interim analysis, saving the remaining 0.0498 alpha for the final analysis. Criteria for the review and any decision will be agreed with the DSMB. A small group of Tolerion management who are not related to the conduct of the trial will be provided unblinded data results from this interim analysis for administrative purposes. This list of individuals to be unblinded will be identified, and the process for these individuals to receive unblinded data results will be finalized prior to the unblinding for this interim.

Unblinded data summaries including safety outcomes and efficacy assessments will be prepared for the sponsor during the study using all data collected through Week 36. A final analysis of the data will be conducted at 52 weeks.

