#### **13.3.2 Safety Analysis**

All randomized subjects who received treatment will be included in a final safety data analysis which will include all data through Week 52 as the as-treated cohorts. In addition to descriptive summaries of all AEs by treatment group, Fisher's Exact test will be used to compare the incidence of the most frequent AEs or SAEs between treatment groups. The MedDRA system will be used to map each AE verbatim term to the system organ class (SOC) and preferred term (PT) for summary purposes. AE data, including the AE verbatim term and the associated AE preferred term, will be provided in the subject data listings. Note that once enrollment of TOL-3021 studies is expanded to adolescent participants aged 12.0 to <18 years of age, data from adolescent participants will be summarized and presented separately from data on adult participants in all subsequent DSMB review meetings.

Adverse event incidence summaries, including incidence rates of SAEs and TEAEs, will be generated on a monthly basis on live data. These will be reviewed in real time by the Sponsor and Emmes, with the treatment groups labeled as "A" and "B." An excessive rate in any specific AE or SAE may result in referral to the DSMB for review. The study statistician will maintain these reports and all resulting correspondence. The code may be requested to be broken by the DSMB after receiving Sponsor approval.

Other safety data, such as laboratory data, physical examination data, and abnormal findings, will be tabulated and/or graphically displayed. Concomitant medications used during the study will be summarized. Medications discontinued prior to the randomization date will be excluded from the summary.

Safety data collected after Week 52 will be analyzed separately from safety data collected during the controlled trial period.

After 6 subjects aged 14-<18 years of age have been enrolled with the last subject having a minimum of 2 injections with at least 1 week follow-up after the 2nd injection. Safety data from these initial subjects will be evaluated before opening the study to subjects 12 and older.

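### Section 3's recipient list for the in-study unblinded summaries leaves out the DSMB, and nothing in the protocol assures the board by-arm safety data after the 30-subject interim

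*Protocol*

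**What the plan says.** **Summaries and recipients.** Three places describe unblinded summaries produced during the study.

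- Section 3 (Trial Design): they "will be prepared for the sponsor during the study using all data collected through Week 36". The paragraph then closes the list of recipients: "The data summaries are unblinded to Sponsor and Emmes, the CRO, only".
- Synopsis (Data Handling and Blinding): they "will be prepared for the sponsor during the study using all data collected through Weeks 24 and 36". There is no restriction to named recipients.
- Section 13.2 (Interim Data Analysis): "Unblinded data summaries including safety outcomes and efficacy assessments will be prepared for the sponsor during the study", again at Week 36. The DSMB is not named as a recipient.

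**Blinding after Week 24.** Section 3 makes the trial triple-blind up to the Week 24 analysis and group-unblinds the sponsor after it. From there, "The study will continue through Week 52 as double-blind with site staff and subjects blinded". Section 8.2.5 has weekly injections for 52 weeks.

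**The DSMB.** Section 5.4 has it review safety data and recommend whether the study continues, stops or changes. Section 13.3.2 says of the treatment code: "The code may be requested to be broken by the DSMB after receiving Sponsor approval".

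**The concern.** The DSMB is the independent body charged with recommending continuation or termination. An imbalance in harm between arms can be seen only in data split by arm. Read as written, Section 3 gives that split to the sponsor and the CRO and to nobody else, at a time when subjects are still being dosed. If the board wants the split itself, Section 13.3.2 makes it ask the sponsor first. Section 5.4 adds that the sponsor's view prevails when the two cannot agree, which makes it more important that the board has its own assured access to the evidence.

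The stake is safety oversight between the first unblinded summary and Week 52. The primary test and its error rate are not affected.

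**Working it through.** The protocol gives no figure to reproduce on this point. The check sets the relevant sections side by side and then bounds the exposure.

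**1. Is the omission deliberate wording or a loose sentence?** The same Section 3 paragraph names the DSMB as a recipient of the 30-subject interim results, together with a limited number of sponsor staff not running the trial. The authors therefore named the board where they meant it. Two sentences later the list for the summaries names two parties and ends with the word only.

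**2. Which summaries are covered?** Sections 3 and 13.2 mention Week 36. Week 24 appears only in the synopsis, which carries no restriction. The sponsor's group unblinding after the Week 24 analysis is, however, stated in Section 3.

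**3. Does another route assure the DSMB by-arm data after the interim?**

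| Route | Where | By-arm to the DSMB? |
|---|---|---|
| Interim and cumulative data on study-related AEs | 5.4 | Format not stated |
| Cumulative AE reports | 11.8.3.1 | Left to the charter |
| Quarterly SAE reports | 11.8.3.2 | Format not stated |
| Cumulative safety data at periodic meetings | 11.8.3.3 | Format not stated |
| Monthly AE incidence by coded group A and B | 13.3.2 | Reviewed by sponsor and CRO; referral to the DSMB is discretionary |
| Breaking the code | 13.3.2 | On request, after sponsor approval |

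No row gives an assured split by arm.

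**4. Is the DSMB unblinded even at the interim?** The synopsis says that unblinded interim results go to the DSMB. Section 13.2 says that the board's review is blinded. Section 13.3.2, by making code-breaking depend on sponsor approval, also describes a board that does not hold the code. These statements cannot all stand. Even on the favourable reading, the interim covers 30 / 99 = 30% of the maximum enrolment.

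**5. How much dosing remains?** The first dose is at randomization (Week 0), so 52 weekly doses fall at Weeks 0 to 51.

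- From Week 24 on: 52 − 24 = 28 doses.
- From Week 36 on: 52 − 36 = 16 doses.

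Both are ceilings. Section 13.3 starts the primary analysis only after all enrolled participants have completed Week 24, and Section 12.5 adds data cleaning and a freeze. Early enrollees may have few doses left, or none.

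**6. Why the split matters (invented example, not a protocol figure).** With 99 subjects at 2:1, the arms are 66 and 33. Suppose 10 subjects have an SAE.

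- All on active: 10/66 = 15.2% against 0/33 = 0%. The difference is 15.2 points (Newcombe 95% CI 2.8 to 25.7; Fisher exact p = 0.028). The pooled rate is 10/99 = 10.1%.
- Equal rates: 10.1% in each arm, about 6.7 and 3.3 expected events. The pooled rate is again 10.1%.

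A pooled table cannot tell these two cases apart.

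**The case against.** **The word only may be aimed at sites and subjects.** The paragraph opens with the blinding of subjects and investigators, the DSMB has already been dealt with as a recipient of the interim, and the parallel texts in the synopsis and Section 13.2 carry no such restriction. This is a plausible account of the intent. It does not remove the problem: the literal list still excludes the board, and Sections 13.2 and 13.3.2 both describe a blinded DSMB. A charter should not have to contradict the protocol.

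**The charter may already provide the split.** This stands. A reader might infer that the DSMB sees only pooled numbers, or knows less about harm by arm than the sponsor. The protocol does not say so. It leaves the format of the board's AE and SAE reports open, and the charter is not available.

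**The monthly coded-group tables would show a marked imbalance.** They would, but to the sponsor and the CRO. Section 13.3.2 says only that an excessive rate may lead to referral. The tables soften the concern without giving the board its own view.

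**The CRO.** A reader might infer that Section 3 unblinds the whole CRO, field monitors and data managers included, in conflict with "Selected Emmes staff will have access to treatment assignments" earlier in the same paragraph. The documents do not support that. The earlier sentence concerns subject-level assignments and the later one concerns group summaries, so they do not contradict each other, and Section 7 leaves the assignments with the unblinded statistician. What stands is narrower: Section 3 limits sponsor access at the interim to staff not directly involved in running the trial, but states no comparable limit for these later summaries.

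**Adolescents.** Sections 5.4 and 13.3.2 require adolescent data to be shown separately at later DSMB meetings. That is a split by age, not by arm, but it does not allow the conclusion that adolescents are singled out for weaker oversight.

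**Conclusion.** The point holds as a defect in a stated distribution rule. Followed as written, Section 3 withholds from the DSMB the unblinded summaries that the sponsor and CRO receive, and no other section assures the board by-arm safety data after an interim on at most 30% of the planned maximum. On that interim itself, the synopsis and Section 13.2 contradict each other.

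The size is bounded by the dosing still to come: at most 28 weekly doses per subject after Week 24 and 16 after Week 36, and fewer in practice. The restriction is explicit for Week 36. It reaches Week 24 only if the summaries listed in the synopsis are read together with Section 3. No harm signal is shown or implied, and the 10 against 0 example only illustrates why pooled counts are not enough. The conclusion assumes that the charter does not override the protocol; if it gives the board by-arm tables, the remaining fault is that the protocol text conflicts with it. The change should be made, because it is cheap and bears on safety oversight.

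**What to change.** 1. In Section 3, replace the closing sentence on recipients, and align the synopsis and Section 13.2 in both recipients and timing. Suggested text: *The unblinded summaries at Weeks 24 and 36 are provided to the DSMB, to the sponsor and to designated unblinded CRO staff. Before the Week 54 database freeze they are not released to sites, to subjects or to CRO staff who perform site monitoring or data queries, except as regulatory reporting requires.* Week 54 is the freeze that Section 12.5 provides for, and the exception keeps the sponsor's reporting duties in Section 11.8.3.2 intact.
2. Reconcile the synopsis and Section 13.2 on whether the DSMB is unblinded at the 30-subject interim, and state the answer once.
3. Amend Section 13.3.2 so that the DSMB can see by-arm safety data without sponsor approval, and carry the same rule into the charter.

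The cost is a few sentences in the protocol and a matching charter entry. The summaries are already planned, so no new analysis is needed. The one small burden is that the CRO must keep a restricted distribution list.
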